### **B.2. Treatment effects on PROs and ecological measures**

Secondary analyses will compare differences in discrete changes in PROs from week 0 to 16 and trajectories of change based on intensive time-series ecological measures between the Lumen and waitlist control groups. Analyses of the treatment effects on PROs will employ the same *t* test approach as described above for testing Criterion 1 for target engagement.

Longitudinal mixed modeling will be applied to analyses of the ecological measures (mood, stress, appraisal, and coping) where the design is  $\text{Group} \times \text{Time} = 2 \times 8$  as these measures will be obtained (using a validated measurement burst design) daily for 7 days every 2 weeks (on weeks 0, 2, 4, 6, 8, 10, 12, 16). During active treatment in the Lumen group, this will occur for 3 days prior to, the day of, and 3 days after each scheduled PST session. For waitlist controls, this will occur for 7 days starting on Sunday of each assigned week. This allows us rich and detailed information on ambulatory changes over the course of treatment, as well as estimates of proximal responses to treatment within 3 days immediately post a PST session. For example, using the means of ecological measures over the 3 pre-PST days (to avoid confounding estimates with proximal treatment response) in the Lumen group and the first 3 days in the waitlist control group every 2 weeks as DVs, we will characterize their trajectory of change in terms of orthogonal linear, quadratic, and cubic components. We also will examine regression spline versions of these trajectories for visualization and interpretation. In a more exploratory vein, for each set of 7 daily ecological measures, collected biweekly, we will use piecewise linear models to characterize proximal responses to treatment based on the change of the 3 post-treatment days' means from the 3 pre-treatment days' means (omitting treatment day 4) in the Lumen group and the corresponding biweekly change of the last 3 days' means from the first 3 days' means (omitting day 4) in the waitlist control group. As these differences are nested within the 8 biweekly measurement bursts, and thus can be examined longitudinally, we can consider whether there is change over weeks in patients' proximal responses to each PST session (in terms of the ecological measures). In all analyses, all available data for each DV will be used and missing data will be handled directly through maximum-likelihood estimation via mixed modeling, supplemented with imputation and sensitivity analysis (see Handling Missing Data in Section B.4 below).

### **B.3. Dose effect analysis**

#### ***B.3.a. Rationale for a standard dose***

Participants randomized to the Lumen treatment group will complete 8 scheduled sessions (4 weekly and then 4 biweekly) over 12 weeks using secure study iPads. The essential research question under study is whether the AI agent Lumen as a new form of PST delivery can meaningfully engage *a priori* neural targets as putative mechanisms of treatment for adults with moderate depressive and/or anxiety symptoms. Fairly extensive evidence has been gathered to establish the optimal dose for implementation of PST in general medical and community settings; this typically involves 6-8 sessions that are initially weekly and taper off to every 2-4 weeks over 12 weeks. Because this is a proof-of-concept project to develop an AI PST agent, we will design and train Lumen to emulate the standards developed for face-to-face delivery of one standardized, empirically supported dose. Dosing comparisons are thus made relative to appropriate implementation of PST and examination of differences in actual delivery (i.e., primarily number and length of sessions and, secondarily, indicators of intervention delivery fidelity).

#### ***B.3.b. Definitions of primary and secondary dose measures***

Two primary dose measures will be the number of PST sessions and the length of PST sessions (in minutes) that participants complete with Lumen. Secondary dose measures will be each of the 2 primary measures weighted by the level of treatment fidelity. All Lumen-based PST sessions will be recorded and independently rated for fidelity by 2 PST master trainers using the validated 7-item PST Adherence and Competence Scale (PST-PAC).

In psychotherapy outcome research, dose is typically defined as the number of sessions of therapy as it is a natural quantitative unit of treatment applicable across types of psychotherapy. In this study, we also include the length of sessions as a measure of dose because (1) it is possible that the number of sessions varies little among participants given the brevity and controlled delivery of the therapy and (2) session length is an important parameter for possible optimization of Lumen to improve participant engagement and efficacy. Note that these dose measures are defined at any stage of the treatment; for example, after 4 sessions have been offered, a participant might have attended 3 sessions (number) for a total of 118 minutes (length). In other words, the dose measures are time-related variables.

Similarly, therapeutic fidelity is another important parameter for optimization in Lumen. In our view, it is a proxy to the strength of medicine and its use in this context adjusts the implied assumption that one session (or the same length of a session) equals one unit or dose, except that the strength (potency) of active ingredients in psychotherapy cannot be measured or standardized in the same way as that of a medication. Although the level of fidelity may be defined differently (e.g., with varying weights of the item scores), the ratio of raw total score to the maximum is simple and easy to interpret and there is no empirical support, to our knowledge, for an alternative. Alternative definitions may be explored using data from this study, especially if they would provide a more nuanced understanding of the need for optimization of Lumen. We will construct fidelity-weighted versions of the dose measures, number and length, in order to adjust doses for conformance to standard PST. Assessing dose in the multiple ways as we propose will allow us to determine which measure is most accurate and to be employed in Study 2. Also, our methodology and results will make an important contribution as assessing dose effects of novel digital health interventions on mechanisms such as brain targets is complex and understudied.

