#### ***B.3.c. Dosing analyses***

Dosing analyses will be conducted **within the Lumen treatment group**. The primary dosing analysis will examine the relationship of neural target activation in the amygdala and DLPFC to the 4 measures of dose (number and length of PST sessions, fidelity-weighted number and length of PST sessions). The secondary dosing analysis will examine the relationship of PROs, ecological end-of-day assessments, and measures of treatment progress (e.g., PHQ9 and GAD7 across PST sessions) to the same 4 measures of

dose. Note that given neural target activation measures and PROs are obtained at weeks 0 and 16, these analyses will focus on change over the full 16-week span of the study, whereas ecological end-of-day assessments and treatment progress measures are available for a total of 8 occasions each, and thus will be considered longitudinally.

**Neural targets:** The primary dosing analyses will consist in the separate regressions of change in activation from week 0 to 16 for the amygdala and DLPFC on each dose variable. This results in 8 separate regressions: amygdala on number of sessions, amygdala on length of sessions, amygdala on fidelity-weighted number, amygdala on fidelity-weighted length, and also DLPFC on the same 4 dose variables. Assumptions of linear regression will be verified and corrected through data transformation as needed. Our purpose is to identify variants of the dose variables with the strongest association (i.e., highest  $R^2$ ) with change over 16 weeks in the 2 neural targets. If the coefficient for dose in these regressions is positive and significant, it confirms that the dose variable is associated with higher change in neural target activation.

**Patient-reported outcomes:** Depression and anxiety symptoms, functioning, and health-related quality of life will be measured at week 0 and 16. Thus, the secondary dose analysis for PROs mirrors the primary analysis for neural targets. That is, change from week 0 to 16 in the PROs will be separately regressed on the 4 dose variants, resulting in separate PRO-dose measure regressions. As in the primary analysis, our purpose is to identify variants of the dose variables with the strongest association (i.e., highest  $R^2$ ) with change over 16 weeks in the PROs of interest.

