**Ecological end-of-day assessments:** Ecological measures of mood, stress, appraisal, and coping will be available at weeks 0, 2, 4, 6, 8, 10, 12 and 16 (for a total of 8 occasions). Each week's assessment is based on 7 contiguous days' end-of-day assessments of the 4 ecological measures, with day 4 being the day of PST treatment in the Lumen group. Thus, the mean of the 3 pre-treatment days on these variables provides an indication of a participants' status immediately prior to each PST session; the mean of the 3 post-treatment days on the same variables provides an indication of a participants' status immediately post the session. For this secondary dosing analysis, we can mirror the dosing analysis by regressing change in the 7-day mean from week 0 to week 16 for each of the 4 ecological measures on the 4 dose variants. Importantly, there are 6 intermediate measurement occasions in addition to week 16, so we will be able to examine trajectories of change from week 0 to week 2, to week 4, and so on, to week 16. Moreover, for each ecological measure a set of time-related variables may be constructed, such as overall 7 days' means, 3 pre-treatment days' means, and differences between 3 pre-treatment days' means and 3 post-treatment days' means (omitting treatment day 4), so we will be able to examine trajectories of change in these variables. It is also important to note that the 4 dosing variables in these longitudinal regression models reflect the dose received up to that point in the treatment. This provides a view of how accurately the dosing variables perform for the ecological measures over the entire span of the treatment. These analyses will use time-varying mixed models where the DV (e.g., mood) and the dose measure vary over the 16-week period. The models for each dose measure (e.g., number of sessions) will include separate polynomial terms for linear, quadratic, and cubic rates of change in the DV over time. Alternatively, we will model the log of the dose measure (e.g., number of sessions) considering that some studies of in-person psychotherapy reported a negatively accelerated relationship between dose and treatment progress, suggesting a pattern of successively diminishing returns with increasing dose. We will compare model fit for the polynomial and logarithmic models using Schwartz Bayesian Information Criterion (BIC).

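### The length dose is total minutes, so unless attendance is nearly uniform the week 0-16 dosing regressions cannot separate session length from number of sessions

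*Combined protocol and SAP*

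**What the plan says.** Appendix 3, B.3.b, names two primary dose measures: the number of sessions and "the length of PST sessions (in minutes) that participants complete with Lumen". It gives two reasons for the second. One is that "it is possible that the number of sessions varies little among participants given the brevity and controlled delivery of the therapy". The other is that "session length is an important parameter for possible optimization of Lumen to improve participant engagement and efficacy". The only worked example shows how length is counted: "a participant might have attended 3 sessions (number) for a total of 118 minutes (length". B.3.c agrees that dose accumulates: "the 4 dosing variables in these longitudinal regression models reflect the dose received up to that point in the treatment". Fidelity-weighted versions of both measures are added as secondary doses.

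For the neural targets, B.3.c plans "separate regressions of change in activation from week 0 to 16 for the amygdala and DLPFC on each dose variable", for example "amygdala on number of sessions, amygdala on length of sessions". The PRO analysis follows the same pattern. The variants are then compared by R-squared, and B.3.b says the comparison will help decide which measure to carry into Study 2. No variable for minutes per session is defined, and no planned model contains number and length together.

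**The concern.** The second reason for including length concerns how long a session should be. The measure as defined answers a different question: how many minutes of treatment a participant received in all. Four sessions of 40 minutes and eight sessions of 20 minutes both score 160, although these are the two formats that anyone choosing a session length would need to tell apart.

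Because each dose is entered alone, a positive length coefficient can arise from attending more sessions, from longer sessions, or from both. When attendance varies, an effect of attendance can show up under the label of length, and a real effect of session length can be diluted by variation in attendance. Fidelity-weighted length has the same structure. What is at stake is any statement about session length that is taken from this pilot into the design of Lumen for Study 2.

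**Working it through.** **The plan's own figures.** Two neural targets times four dose measures gives 2 x 4 = 8, matching "This results in 8 separate regressions". The worked example gives 118 / 3 = 39.3 minutes per session, so the 118 is a cumulative total.

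**Inputs from the documents.** There are 40 Lumen participants and at least 85% retention, so 0.85 x 40 = 34 are analysed. The maximum is 8 sessions. The acceptability milestones (section 3.0, Aim 2) are at least 95% completing one or more sessions and at least 80% completing four or more.

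**Assumptions, because the documents are silent.** N is the number of sessions and L a participant's mean session length, taken as independent. The between-person CV of L runs from 0.10 to 0.40. Three attendance patterns are used:
- Milestone floor: 5% attend none, 15% are spread evenly over 1-3, and 80% evenly over 4-8. Mean = 0.05 x 6 + 0.16 x 30 = 5.10; variance = 31.10 - 5.10² = 5.09; CV of N = 2.26 / 5.10 = 0.44.
- Good attendance: 70% complete 8 and 30% are spread evenly over 4-7. Mean 7.25, SD 1.30, CV 0.18.
- Near-uniform: 90% complete 8 and 10% complete 7. Mean 7.9, SD 0.3, CV 0.04.

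**Overlap.** For total minutes T = N x L:

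corr(T, N) = 1 / sqrt(1 + CV_L² (1 + 1/CV_N²))

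corr(T, L) = 1 / sqrt(1 + CV_N² (1 + 1/CV_L²))

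At the floor with CV_L = 0.20, corr(T, N) = 1 / sqrt(1 + 0.04 x 6.1) = 0.90, and corr(T, L) = 1 / sqrt(1 + 0.195 x 26) = 0.41.

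| Attendance | corr(T, N), CV_L 0.10 / 0.20 / 0.30 / 0.40 | corr(T, L), same CV_L |
|---|---|---|
| Milestone floor | 0.97 / 0.90 / 0.80 / 0.71 | 0.22 / 0.41 / 0.54 / 0.64 |
| Good | 0.87 / 0.66 / 0.51 / 0.40 | 0.49 / 0.74 / 0.85 / 0.90 |
| Near-uniform | 0.35 / 0.19 / 0.13 / 0.09 | 0.93 / 0.98 / 0.99 / 0.99 |

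**Consequence at n = 34.** This was simulated with a standardised slope of 0.45, CV of session length 25% between persons and 20% within, and a two-sided 0.05 level. The planned regression on T alone is set against mean minutes adjusted for number.

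| Attendance | Only number matters: T significant | Same: adjusted mean minutes | Only session length matters: T significant | Same: adjusted mean minutes |
|---|---|---|---|---|
| Milestone floor | about 62% | about 5% | about 23% | about 67% |
| Good | about 31% | about 5% | about 56% | about 72% |
| Near-uniform | about 6% | about 5% | about 71% | about 72% |

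**Longitudinal models.** Number and total minutes both grow over time. Pooled over eight occasions with full attendance, their correlation is 0.98 / 0.92 / 0.84 / 0.75 for CV_L 0.10 / 0.20 / 0.30 / 0.40. Uniform attendance therefore does not separate them there.

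**The case against.** A reader might infer that total minutes merely re-measures the number of sessions and can say nothing about session length. The documents do not support that. The plan's first reason for using length is that number may hardly vary. In that case total minutes is almost a pure measure of session length in the week 0-16 regressions (correlation 0.93 to 0.99), and the false-signal rate stays near nominal.

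A reader might also infer that Study 2 will be misdirected. That is not shown either. The plan compares dose variants by R-squared and does not read one p-value in isolation. In simulations at n = 34, slope 0.45 and session-length CV of 15-35%, when only number matters the number regression has the higher R-squared in 71-84% of trials at the milestone floor and 84-92% with good attendance. When only length matters, total minutes has the higher R-squared in 66-79% and 79-90%. The plan also says only that a significant coefficient shows an association with that dose variable. It nowhere promises to read it as the effect of longer sessions. Total minutes is a legitimate exposure dose and fits the cumulative longitudinal models, which mean minutes does not.

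All of this stands, and it limits the point. It does not remove it. The plan calls low variation in number only possible, B.3.c itself allows that some participants will stop early, and the milestones tolerate up to 20% completing fewer than four sessions. Ranking two overlapping variables by R-squared gives a hint about which component matters, but no estimate of a session-length effect.

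**Conclusion.** The point holds in a limited form. The length dose is number of sessions times mean minutes per session and is analysed alone. Unless attendance is nearly uniform, its week 0-16 coefficient mixes the two, and the planned regressions cannot isolate the parameter that B.3.b says may be optimised.

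The definition and the model structure come straight from the text. The size does not: it rests on assumed attendance patterns, an assumed spread of session length, independence of the two, and an assumed slope. Across those assumptions, the chance that total minutes is significant when only number matters runs from about 6% (near-uniform) to about 62% (milestone floor, the least favourable attendance that still meets the milestones).

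The stakes are moderate. These are within-arm dosing analyses and lie outside the two target-engagement criteria. The gap matters for what may be said about session length, and it is cheap to close.

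**What to change.** In B.3.b, state that length means total minutes to date. Keep it as the cumulative exposure dose, including in the longitudinal models for the ecological and treatment-progress measures, and say that its coefficient is not to be read as a session-length effect.

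In B.3.c, add for each neural target and each PRO a week 0-16 model with number of sessions and mean minutes per completed session entered together. Add the fidelity-weighted counterpart, with its divisor stated. Base any statement about session length on these models.

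No new data are needed: the schedule of measures in Appendix 2 already records the number and duration of completed sessions. The costs are:
- One extra regression term at about 34 participants.
- Participants with no session have no mean length and drop out of the added model. At the milestone floor this is 5% of 34, or about two people. They stay in the number-only regression.
- Mean length may depend somewhat on number, because Appendix 1, Section A, describes session 1 as an introductory session whose length may differ. The correlation between number and mean length should be reported beside the added models.

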#### ***B.3.c. Dosing analyses***

Dosing analyses will be conducted **within the Lumen treatment group**. The primary dosing analysis will examine the relationship of neural target activation in the amygdala and DLPFC to the 4 measures of dose (number and length of PST sessions, fidelity-weighted number and length of PST sessions). The secondary dosing analysis will examine the relationship of PROs, ecological end-of-day assessments, and measures of treatment progress (e.g., PHQ9 and GAD7 across PST sessions) to the same 4 measures of

dose. Note that given neural target activation measures and PROs are obtained at weeks 0 and 16, these analyses will focus on change over the full 16-week span of the study, whereas ecological end-of-day assessments and treatment progress measures are available for a total of 8 occasions each, and thus will be considered longitudinally.

**Neural targets:** The primary dosing analyses will consist in the separate regressions of change in activation from week 0 to 16 for the amygdala and DLPFC on each dose variable. This results in 8 separate regressions: amygdala on number of sessions, amygdala on length of sessions, amygdala on fidelity-weighted number, amygdala on fidelity-weighted length, and also DLPFC on the same 4 dose variables. Assumptions of linear regression will be verified and corrected through data transformation as needed. Our purpose is to identify variants of the dose variables with the strongest association (i.e., highest  $R^2$ ) with change over 16 weeks in the 2 neural targets. If the coefficient for dose in these regressions is positive and significant, it confirms that the dose variable is associated with higher change in neural target activation.

**Patient-reported outcomes:** Depression and anxiety symptoms, functioning, and health-related quality of life will be measured at week 0 and 16. Thus, the secondary dose analysis for PROs mirrors the primary analysis for neural targets. That is, change from week 0 to 16 in the PROs will be separately regressed on the 4 dose variants, resulting in separate PRO-dose measure regressions. As in the primary analysis, our purpose is to identify variants of the dose variables with the strongest association (i.e., highest  $R^2$ ) with change over 16 weeks in the PROs of interest.

**Ecological end-of-day assessments:** Ecological measures of mood, stress, appraisal, and coping will be available at weeks 0, 2, 4, 6, 8, 10, 12 and 16 (for a total of 8 occasions). Each week's assessment is based on 7 contiguous days' end-of-day assessments of the 4 ecological measures, with day 4 being the day of PST treatment in the Lumen group. Thus, the mean of the 3 pre-treatment days on these variables provides an indication of a participants' status immediately prior to each PST session; the mean of the 3 post-treatment days on the same variables provides an indication of a participants' status immediately post the session. For this secondary dosing analysis, we can mirror the dosing analysis by regressing change in the 7-day mean from week 0 to week 16 for each of the 4 ecological measures on the 4 dose variants. Importantly, there are 6 intermediate measurement occasions in addition to week 16, so we will be able to examine trajectories of change from week 0 to week 2, to week 4, and so on, to week 16. Moreover, for each ecological measure a set of time-related variables may be constructed, such as overall 7 days' means, 3 pre-treatment days' means, and differences between 3 pre-treatment days' means and 3 post-treatment days' means (omitting treatment day 4), so we will be able to examine trajectories of change in these variables. It is also important to note that the 4 dosing variables in these longitudinal regression models reflect the dose received up to that point in the treatment. This provides a view of how accurately the dosing variables perform for the ecological measures over the entire span of the treatment. These analyses will use time-varying mixed models where the DV (e.g., mood) and the dose measure vary over the 16-week period. The models for each dose measure (e.g., number of sessions) will include separate polynomial terms for linear, quadratic, and cubic rates of change in the DV over time. Alternatively, we will model the log of the dose measure (e.g., number of sessions) considering that some studies of in-person psychotherapy reported a negatively accelerated relationship between dose and treatment progress, suggesting a pattern of successively diminishing returns with increasing dose. We will compare model fit for the polynomial and logarithmic models using Schwartz Bayesian Information Criterion (BIC).

**Treatment progress measures:** To monitor treatment progress, symptoms (PHQ9, GAD7) and treatment acceptability (usability, user experience, and treatment alliance) will be measured in each PST session at weeks 1, 2, 3, 4, 6, 8, 10, and 12 (for a total of 8 occasions). Similar to the analyses of ecological measures as described above, we will implement polynomial and logarithmic models and compare model

fit using BIC. These regressions'  $R^2$ 's will allow us to examine in detail the relationship of treatment progress and cumulative dose, with fidelity-to-PST taken into account using the fidelity-weighted number and length of PST sessions. Additionally, as is common in psychotherapy in general, it is possible that not all participants will complete the full 8 sessions as some may drop out early owing to either lack of improvement or “enough” improvement based on self-assessment or yet other reasons related or unrelated to the treatment. Using the Good-Enough-Level (GEL) model, some studies of in-person psychotherapy showed that the rate of change varied as a function of treatment duration, namely, the rate of change (progress) was faster for patients attending fewer sessions but slower for those attending more sessions. In other words, patients may remain in treatment until they improve. To explore whether a similar pattern is present for Lumen PST, we will apply the GEL modeling approach by extending the polynomial models for treatment progress measures, in particular, PHQ9 and GAD7, to include a fixed effect of total treatment dose (e.g., total number of sessions) and interactions between total treatment dose and linear, quadratic, and cubic rates of change. Essentially, the GEL model is a stratified analysis that examines dose effects across strata of participants with similar treatment dose (e.g., similar number of sessions attended), as opposed to aggregate dose effects across all participants. Furthermore, we will conduct exploratory analyses of baseline characteristics in relation to the dose effects on neural targets, PROs, ecological measures, and treatment progress measures. We anticipate that baseline characteristics (e.g., severity at presentation, sex as a biological variable, sociodemographics) may be related to dosing estimates (e.g., via actual sessions completed). To explore these relationships, baseline characteristics and their interactions with dose measures will be added to the models as described above.

